Q2: What are the moderators and mediators of the effectiveness of Concussion Coach?

- (a) Is comfort with technology related to efficacy of Concussion Coach?
- (b) Is perceived social support related to efficacy of Concussion Coach?

Q3: Does use of Concussion Coach (a) increase Veterans' knowledge about TBI and change Veterans' attribution of symptoms from mild TBI to less "pathological" explanations (e.g., stress, post-deployment re-adjustment, or other causes), (b) increase Veterans' self-efficacy in coping with symptoms?

More broadly, are the effects of Concussion Coach on PCS and psychological distress mediated through change (from T1 to T2) in Veterans' perceptions and knowledge of the illness and in self-efficacy?

Q4: What aspects of Concussion Coach are most associated with positive outcomes among recipients of Concussion Coach? Is more frequent use of specific components of Concussion Coach associated with greater improvement, relative to other components?

Q5: What are the factors associated with use of Concussion Coach or with deriving benefit from use of Concussion Coach that can be used to inform future modifications of the application and wide scale implementation?

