5.0 Study Procedures

5.1 Study Design

- Describe experimental design of the study. Include sequential and/or parallel phases of the study, including durations, and explain which interventions are standard of care.
- Include a description of how anticipated risk will be minimized and include an analysis of risk vs. potential benefit.
- Provide description of the study population (delineate all categories of subjects – patients, providers, family members, employees, etc.). Include anticipated enrollment numbers
- As applicable, provide information on any added protections for vulnerable populations.
- If applicable include information on data.

Patients who meet eligibility criteria and consent to participate in the study are randomly assigned to one of two arms, either the Concussion Coach group, which will receive the Concussion Coach "Explorer" version either downloaded onto their own smart phone or via an iPod touch® given them for this purpose or the no mobile app control group. Study personnel will explain the purpose of the study, complete the informed consent process in person or over the telephone, obtain the random treatment assignment and introduce the participant to his/her baseline evaluator, if appropriate. The random assignment to intervention will be accomplished in blocks within each site. While small block sizes allow intervention group sizes to be very similar it may make the allocation process predictable. Therefore, to reduce selection bias and achieve balance across the intervention arms, a sequence list of individual assignments by random block sizes will be generated.

Both groups will be assessed in a pre/post intervention design and will be compensated for completing study questionnaires. During the time that they are involved in the study, the intervention group will be sent (via Concussion Coach) reminders to engage with the App. Their use (e.g., total time spent on each component of the App) will be collected electronically. Both

Version:13 05/31/2018

groups will receive care as usual (meaning their regularly scheduled VA appointments and medications). At the completion of the study, both groups will be encouraged to download the App for their own use, with assistance from the study team if needed (see Figure 2).

Description of Intervention & Training

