5.6 Data Analysis

[figure not shown]
Sample Size Justification: Below is a diagram of the expected subject recruitment and attrition (see Figure 2). Our recruitment estimates are based on our experience with prior trials (e.g., a recent pilot study of a web based intervention successfully recruited over 90% of potential participants) and our emphasis in the budget of recruitment personnel who will be embedded in our clinics. We conservatively estimate that 60% of potential participants will agree to participate and be successfully enrolled in the study. Our attrition estimate of 20% is based on our experience with an internet self-help intervention study, during which drop out was less than 20%. This was accomplished through continued outreach by the recruiter via letter and calls. Based on these conservative numbers and a recruiting period of 33 months we expect a minimum N=388 participants in the study [(20 newly identified participants per month over 33 months + 150 existing) *60% participation* (1-20% attrition)]. This is a conservative estimate

because we have excluded the existing 1,332 potential participants living in our area (national dataset) to whom we will mail letters.

For each regression model proposed for H1&2, results of sample size calculation using the application PASS v11 (Hintze, 2011) show that a much smaller N=148 (or N=194) achieves 80% (or 90%) power to detect an additional R-Squared of 0.05 (proportion of explained variation in the outcome) attributed to 2 independent variables (TBI Coach plus an interaction) using an F-Test with alpha of 0.05. This assumed the variables tested are adjusted for 10 independent variables with an R-Squared of 0.20.

We note that of all statistical models proposed in this study, the mediation model has the most stringent sample size requirement. With conservative total N=388, we expect to have greater than .80 power to detect a small to medium effect size of the mediated effect at alpha = 0.05. The two regression coefficients (beta1 & beta2) that jointly capture the mediated effects are critical in the power calculation for a mediation

Figure 2. Expected Total Recruitment

model. Using the parameter values of 0.14, 0.39, and 0.59, corresponding to Cohen's criteria68 for small (2% of the variance), medium (13% of the variance), and large (26% of the variance) effect sizes, respectively, Fritz and MacKinnon (2007) conducted empirical estimates of sample

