be performed using the Mplus statistical application which offers alternatives that do not require the regular assumption of symmetric, normal distributions for parameter estimates. Bayesian estimation method with diffuse priors will be used with appropriate posterior simulation schemes based in Markov Chain Monte Carlo (MCMC) methods. One advantage of the MCMC estimation process is that it provides accurate tests of mediated effects for small samples; e.g. by simply taking the product of the two coefficients alpha and beta for every draw and compute its standard deviation across all draws to obtain standard errors of mediated effect. Also, unlike the normal-based ML confidence interval, inference will rely on Bayesian credibility interval based on the percentiles of the posterior, which easily allows for a strongly skewed distribution alphabeta product⁷⁴

Hypothesis 4: More time spent on (a) TBI Coach use, and (b) specific interactive components of TBI Coach (i.e., the "tools" section) will be associated with lower PCS symptom severity after adjusting for baseline PCS values and potential confounders.

Analysis: A regression model of PCS will be performed on the TBI Coach sample only, separately for (a) TBI coach use, and (b) each interactive component as the main predictor. First the PCS baseline score, demographics and other potential confounders will be included in the base model. Then a full model with addition of the time score for one TBI Coach aspect at a time will be fitted. Appropriate transformation (e.g. log) of all time variables will be done as suggested by their general distribution; a significant negative coefficient of the time variable will confirm a negative association between time spent on that component and symptom severity. Standardized coefficient estimates as well as R-sq estimates will be obtained so that all TBI Coach aspect-specific models can be compared on the relative strengths of the aspect-outcome relationships.

As an extension, secondary analysis will be performed on the TBI Coach components that show strong relationship in the expected direction. Each time spent (as a dependent variable) will be regressed on the predictors in the base model to identify both positive and negative contributory factors to the specific component usage.

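### Hypothesis 4 enters each app component's time on its own, so the planned comparison cannot separate a component's own association from use of the rest of the app

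*Combined protocol and SAP*

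**What the plan says.** The analysis paragraph under Hypothesis 4 in section 5.6 Data Analysis restricts the data to one arm: "A regression model of PCS will be performed on the TBI Coach sample only". Models are fitted "separately for (a) TBI coach use, and (b) each interactive component as the main predictor", so total use has its own model and is not a covariate in the component models. The covariates are set first: "First the PCS baseline score, demographics and other potential confounders will be included in the base model". Neither total app time nor time on other components is named among them. The next step is "Then a full model with addition of the time score for one TBI Coach aspect at a time will be fitted". Standardized coefficients and R-squared are reported so that the models "can be compared on the relative strengths of the aspect-outcome relationships".

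The question this is meant to serve is Q4 in section 2.0: "Is more frequent use of specific components of Concussion Coach associated with greater improvement, relative to other components". Nothing in the document fits the components together, adjusts one for the rest, or tests a difference between them.

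**The concern.** Participants who use the app a lot will tend to spend more time on every part of it, and those who do not use it have zero on every part. The protocol expects both kinds: section 5.1 plans interviews with non-users and infrequent users, and the qualitative sample-size text in section 5.6 expects low- and high-volume users. Component times will then be positively correlated, and a model with a single component credits it with whatever the omitted components, or engagement itself, contribute.

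At stake is the advice on which parts of the app to keep or redesign. Section 5.6 also carries components with a strong relationship in the expected direction into a secondary analysis of who uses them, so a false flag would be passed on.

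**Working it through.** **Inputs from the plan.** The expected total is given as "we expect a minimum N=388 participants in the study", from (20 × 33 + 150) × 0.60 × 0.80 = 388.8, which reproduces. Section 5.1 uses blocks "to reduce selection bias and achieve balance across the intervention arms" but states no ratio. Assuming 1:1, the app arm has 388/2 = 194, taken below as n = 190. The plan gives no power for Hypothesis 4. Its N=148 and N=194 belong to Hypotheses 1 and 2, and they reproduce: with f² = 0.05/(1 - 0.20 - 0.05) = 0.067, a noncentral F with 2 and N - 13 degrees of freedom gives power 0.801 and 0.902. From that calculation I borrow alpha 0.05 and a base-model R-squared of 0.20.

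**Assumed inputs.** Four components, equal pairwise correlation ρ of 0.4, 0.6 or 0.8, and a standardized effect of -0.20. The documents give none of these.

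**Is a non-zero correlation plausible?** Suppose users' component times were independent (assumed median 10 minutes, log-SD 1). Non-users at zero would by themselves produce log-time correlations of 0.44, 0.61, 0.70 and 0.76 for 10%, 20%, 30% and 40% non-use.

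**Case A: one active component, the others inert.** Fitted alone, an inert component has expected coefficient -0.20ρ and residual variance 0.76 + 0.04(1 - ρ²), where 0.76 = 1 - 0.20 - 0.04. At ρ = 0.4 the coefficient is -0.08 and the SE is √(0.7936/190) = 0.0646. Then z = 1.24, and the chance of p<0.05 is about 24%.

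**Case B: no component acts, general engagement does.** The expected coefficient is -0.20√ρ and the residual variance 0.76 + 0.04(1 - ρ). At ρ = 0.4 the coefficient is -0.126, the SE 0.0642, z = 1.97, and the chance is about 50%.

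**Adjusting for time on the other three components.** One component correlates with the sum of the other three at 3ρ/√(3 + 6ρ). The variance inflation is therefore 1.36, 1.96 and 3.82, and the SE is multiplied by 1.17, 1.40 and 1.96. At ρ = 0.4 the active component has SE √(0.76 × 1.36/190) = 0.074, z = 2.71 and power 77%. Without adjustment the SE is 0.063, z = 3.16 and power about 88%.

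| Quantity | ρ=0.4 | ρ=0.6 | ρ=0.8 |
|---|---|---|---|
| A: given inert component significant, alone (formula) | 24% | 46% | 71% |
| same, simulated | 25% | 44% | 70% |
| same, adjusted, simulated | about 5% | about 5% | about 5% |
| B: given component significant, alone (formula) | 50% | 68% | 80% |
| same, simulated | 48% | 68% | 78% |
| same, adjusted, simulated | 12% | 9% | 8% |
| A: inert component ranked first, alone, simulated | 11% | 17% | 35% |
| same, adjusted, simulated | 11% | 17% | 34% |
| A: power for the active component, adjusted, simulated | 76% | 63% | 36% |

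If the base model explained no variance (0.96 in place of 0.76), the first row would be 20%, 38% and 61%. This gives the lower end of the range. At ρ = 0 there is no inflation.

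**The case against.** Hypothesis 4 is worded as a marginal association, and the plan says only that a negative coefficient confirms one. The planned models answer that. With about 190 people and correlated predictors, one-at-a-time models are a reasonable exploratory choice, because adjustment costs real power. Every input that drives the size is assumed, including the number of components: Hypothesis 4 names only the tools section. All of this stands. It leaves the gap with Q4, which asks for a comparison between components.

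A reader might go further in three ways that the documents and the calculation do not support.

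- **That Q4 is unanswerable, or that all components will be flagged.** The usage data are collected by component, so other models can address Q4. In case A at ρ = 0.4, at least one of the three inert components is significant in 46% of trials, which is well short of certainty.
- **That the planned ranking is spoiled by the omitted components and adjustment would repair it.** In case A the share of trials with an inert component first is practically the same before and after. With equal correlations this misranking is sampling noise. In case B no component acts, so any order is chance.
- **That adjustment restores the nominal error rate in general.** It does so in case A. In case B it leaves 8-12% per component, and at least one of four is significant in 45%, 35% and 27% of trials.

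**Conclusion.** The point holds in limited form. The planned models answer the marginal Hypothesis 4, but they do not answer whether a component matters relative to the others, and their output cannot tell one active component from general engagement. Under the stated assumptions a given inert component is significant in roughly 20-70% of trials when another is active, and in about 48-78% when only engagement acts. These figures rest on an assumed n of about 190, four components, an effect of -0.20 and correlations of 0.4 to 0.8. Expected non-use makes zero correlation implausible, but the documents do not fix a value.

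This is an observational aim within the app arm. A reader should not infer any effect on the randomised comparison in Hypothesis 1. I rate it a cheap improvement of low severity.

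**What to change.** Keep the one-at-a-time models as the descriptive test of Hypothesis 4. For each component, pre-specify a further model that adds suitably transformed time on all other components. Report the adjusted coefficients with 95% confidence intervals. Rest any claim that one component matters more than another on these and on a test or interval for the difference between coefficients, which a single model holding all components supplies. Do not rest it on rank order. State that residual confounding by engagement remains possible after adjustment.

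Raw component times add up to total time, so all of them and the total cannot enter one model untransformed.

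The cost is a few regressions on data already being collected. The price in precision is intervals about 1.2 to 2 times wider. Power for a truly related component falls from about 87% to 76%, 63% and 36% at correlations of 0.4, 0.6 and 0.8. The observed correlations between component times should be reported so that readers can see how far the data can separate the components.

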3.0 Objectives

The proposed study is a 4-year randomized control trial investigating the utility of an interactive, self-management smartphone application, "Concussion Coach," one of a suite of mobile applications developed by VA. The primary goal of the proposed study is to evaluate the efficacy of Concussion Coach for improving clinical outcomes in those with a history of mild traumatic brain injury (mild TBI) and to determine what aspects of Concussion Coach are most

useful to Veterans. An overarching goal of this line of research is to improve access among Veterans with mild TBI who still have symptoms months to years after injury.

Aim 1. Evaluate the efficacy of Concussion Coach for improving clinical outcomes among recipients of Concussion Coach.

Hypothesis 1 (Primary Hypothesis): Patients randomized to receive Concussion Coach for 3 months will have (a) lower Post-Concussion Symptom severity (PCS) and, (b) lower psychological distress, compared to patients randomized to a no intervention control group, after adjusting for baseline severity and other potential confounders.

Aim 2. Explore mediation/moderation of Concussion Coach effects on clinical outcomes among recipients of Concussion Coach.

Hypothesis 2: The effects of Concussion Coach on PCS (and psychological distress) will be greater for Veterans who have (a) greater comfort with technology at baseline than for those who are less comfortable; (b) greater social support at baseline than for those with less social support.

Aim 3. Determine the aspects of Concussion Coach most associated with positive outcomes.

Hypothesis 3: If Concussion Coach improves Veterans' (a) knowledge about TBI and attribution of symptoms and/or (b) self-efficacy in coping with symptoms, Veterans will have less PCS and psychological distress.

Aim 4. Obtain qualitative information on factors associated with use of Concussion Coach or with deriving benefit from use of Concussion Coach that can be used to inform future modifications of the application and wide scale implementation.

Hypothesis 4: More time spent on (a) Concussion Coach use, and (b) specific interactive components of Concussion Coach (i.e., the "tools" section) will be associated with lower PCS symptom severity after adjusting for baseline PCS values and potential confounders.

Research Question 1: What barriers prevent patients from using the Concussion Coach and from improving on PCS symptom severity?

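### Predictors of app use are modelled only for components that first show a strong favourable link with symptoms; no unconditional model of who uses the app is stated

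*Combined protocol and SAP*

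**What the plan says.** The questions come first. Q5 in section 2.0 reads "What are the factors associated with use of Concussion Coach or with deriving benefit from use of Concussion Coach", to guide later changes to the app and its roll-out. Research Question 1 in section 3.0 asks "What barriers prevent patients from using the Concussion Coach and from improving on PCS symptom severity". Both sit with Aim 4, whose purpose is to "Obtain qualitative information on factors associated with use of Concussion Coach or with deriving benefit from use of Concussion Coach". Aim 4 also carries Hypothesis 4, which is quantitative.

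The analysis is in section 5.6 under Hypothesis 4. In the app arm only, follow-up symptom score (PCS, measured by the NSI) is regressed on usage time, "separately for (a) TBI coach use, and (b) each interactive component as the main predictor". On covariates: "First the PCS baseline score, demographics and other potential confounders will be included in the base model". On interpretation: "a significant negative coefficient of the time variable will confirm a negative association between time spent on that component and symptom severity".

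The extension follows: "secondary analysis will be performed on the TBI Coach components that show strong relationship in the expected direction". For those components, "Each time spent (as a dependent variable) will be regressed on the predictors in the base model", with the aim of finding what raises or lowers use of the particular component. No other regression in the plan has usage as the dependent variable.

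**The concern.** Who uses the app, and what keeps others from using it, can be asked without knowing whether use goes with fewer symptoms. The plan nevertheless lets a component into the usage model only after its time score has shown a strong favourable association with symptoms. Three things follow.

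- The set of components modelled is chosen by an outcome result, and the threshold for that choice is not stated.
- Hypothesis 4 separates total use (a) from components (b), and the extension names only components. On the natural reading, predictors of total app time, the most direct measure of uptake, are not modelled.
- If no component qualifies, no model of use is fitted at all, although the Explorer version logs usage for the app arm.

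The condition also ties the question to participants with a follow-up symptom score, which a model of use does not need. Participants lost to follow-up whose usage was uploaded could inform the question about barriers.

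What is at stake is the quantitative part of the information that is meant to guide revision and roll-out of the app. The primary comparison of the arms is not affected.

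**Working it through.** **The plan's own figures.** The plan gives no sample size for Hypothesis 4 or its extension. The nearest figures, in section 5.6, reproduce.

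- Expected N: (20 × 33 + 150) × 0.60 × 0.80 = 388.8, stated as 388.
- Regression for Hypotheses 1 and 2: R-squared increment 0.05 for 2 tested variables, 10 covariates with R-squared 0.20, alpha 0.05. With f² = 0.05/(1 − 0.20 − 0.05) = 0.0667, noncentrality N × f², and 2 and N − 13 degrees of freedom, power is 0.801 at N=148 and 0.902 at N=194, as stated.

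**Inputs for the check.**

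- App arm analysed: 388/2 = 194. Equal allocation is an assumption, since the ratio is not stated. (That this equals the N for 90% power above is a coincidence.)
- Covariates: 10, borrowed from the power calculation, because the base model is not listed.
- Strong: read as two-sided p<0.05 in the expected direction. This is an assumption; a stricter reading lowers every pass rate.
- Components: four, taken as independent. Section 5.1 lists three components in addition to a Resources section, so three is shown as well where available.
- True association between time and symptoms: unknown, so a range is shown.

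**Chance that one component qualifies.** By the Fisher z approximation, P(pass) = P(Z > 1.96 − atanh(r) × √(194 − 10 − 3)), with √181 = 13.45. The chance that none of four qualifies is (1 − P)⁴.

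| Partial r | atanh(r) × 13.45 | P(pass) | None of four |
|---|---|---|---|
| 0 | 0 | 0.025 | 0.90 |
| 0.05 | 0.67 | 0.10 | 0.66 |
| 0.10 | 1.35 | 0.27 | 0.28 |
| 0.15 | 2.03 | 0.53 | 0.05 |
| 0.25 | 3.44 | 0.93 | below 0.001 |

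The last row is the plan's planning effect carried over to a single time variable: partial r² = 0.05/(1 − 0.20) = 0.0625, so r = 0.25.

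**Second method.** A noncentral F test with one tested variable and the same covariates, n=194:

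| R-squared increment | P(pass) | None of three | None of four |
|---|---|---|---|
| 0.01 | 0.34 | 0.28 | 0.19 |
| 0.02 | 0.60 | 0.06 | 0.03 |
| 0.05 | 0.95 | below 0.001 | below 0.001 |

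With no association, the chance that none qualifies is 0.975³ = 0.93 for three components and 0.975⁴ = 0.90 for four. The two methods agree: an increment of 0.01 is a partial r of √(0.01/0.80) = 0.11.

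**Sensitivity to sample size.** At an increment of 0.01, the chance that none of four qualifies is 0.27 with 150 analysed in the app arm and 0.14 with 225.

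If the usage models were fitted whatever the Hypothesis 4 result, the chance of having no such model would be zero in every row.

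**The case against.** The case for leaving the text alone has substance.

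- **Use is analysed elsewhere.** A reader might infer that use is never analysed. That is wrong: section 5.6 tabulates average time on the app and its components without condition, and total use and each interactive component enter the Hypothesis 4 models as predictors.
- **Non-use is studied.** A reader might infer that only the interviews, covering about 10% of app users, speak to uptake. Sections 5.1 and 5.5 do direct those interviews partly at non-users and infrequent users. But Table 1 also lists the Follow-Up Data Form as a source on barriers and facilitators and does not restrict it to interviewees. Its contents are not shown.
- **Aim 4 is mainly qualitative.** So Q5 as a whole is not left unanswered. Its deriving-benefit half also has quantitative input from the moderation tests under Hypothesis 2, which carry no such condition.
- **Little-used components are not excluded by rule.** The condition concerns association with symptoms. Narrow variation in time would make passing harder, but no usage figure in the documents shows that this will happen.
- **Exclusion of total use is a reading.** The wording on interpreting the time variable speaks of a component while apparently covering total use too, so the term is used loosely.
- **The size depends on chosen inputs.** At the plan's own planning effect a component would pass about 93% to 95% of the time.
- **The extension is secondary.** Asking who uses the components linked to benefit is a coherent exploratory question.

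These points narrow the concern but do not remove it. A table of mean times does not show who used the app, and purposive interviews do not replace a model on data logged across the arm. The extension itself sets out to find contributory factors to use quantitatively, so the plan intends such an analysis and then restricts it.

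**Conclusion.** The point holds in a limited form. The plan states no model of predictors of use that is free of selection on outcome; the selection threshold is undefined; and total app time is, on the natural reading, left out. The modelled answer to the use half of Q5 therefore depends on a symptom result.

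The risk that it is empty is material only if time-symptom associations are small or absent: about 90% with none and 28% at partial r 0.10, falling to 5% at 0.15 and to a negligible level at about 0.25. These figures rest on 194 analysed in the app arm under equal allocation, 10 covariates, a p<0.05 reading of strong, and four independent components. The planning effect was set for two variables jointly under Hypotheses 1 and 2, so using it for a single time variable is itself an assumption.

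Even where some components qualify, the others get no usage model, so the answer remains an outcome-selected one. This is a cheap improvement to an exploratory analysis. It does not threaten the trial's main conclusion.

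**What to change.** In the Hypothesis 4 extension of section 5.6, delete the condition on strength and direction. Prespecify as exploratory:

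- one regression of total app time and one of each component's time, fitted whatever the Hypothesis 4 results;
- as predictors, the base-model variables, listed by name, plus the baseline eHEALS and social support scores already collected;
- as the population, all randomised app-arm participants with usage data, whether or not they completed the second assessment;
- zero use kept in, with a stated method, because a plain log transformation fails at zero. Zero use should be distinguished from usage never retrieved, since section 5.1 relies on Wi-Fi upload or collection at the final visit;
- all models reported, with their number stated.

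If the team still wants to highlight components linked to lower symptoms, it can mark them in the same table under a defined threshold.

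The cost is a change of wording and a few regressions on data already being collected. The downside is a longer exploratory table with more comparisons, which the exploratory label should make plain.
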